#### **7.5.4 Overall Survival**

OS is defined as the time from the date of first dose of study drug to the date of death due to any cause. If a death has not been observed by the date of the analysis cutoff, OS will be censored at the date of last contact.

The survival distribution function for OS will be estimated using the KM method as described for DOR in Section 7.5.2. The OS rate at 2, 4, 6, 8 and 10 months will be estimated with corresponding two-sided 95% CIs.

Frequency counts and percentages of patients with an event (death) and censoring reasons will be summarized. Censoring reasons are as follows:

- Ongoing and no death
- Lost to follow-up

#### **7.5.5 Immune-related Response Rate**

Immune-related RR (irRR) is defined as the proportion of patients who achieve immune-related best overall response (irBOR) of immune-related CR (irCR) or immune-related PR (irPR), as determined by the Investigator per irRC, where irBOR is the best response using irRC recorded from the start of study treatment until the end of treatment.

The confirmed irBOR for each patient is determined from the sequence of overall timepoint (lesion) responses per irRC as summarized in Appendix 6 in the study protocol. The derivation of BOR with confirmation requirement as defined in Section 7.5.1 will be used to determine the

irBOR. In addition, Immune-related PD (irPD) needs to be confirmed by a repeat, consecutive assessment no less than 4 weeks from the first documented date.

The irRR will be calculated along with the two-sided exact Clopper-Pearson 95% CIs. In addition, the number and percentage of patients in each BOR category, i.e., irCR, irPR, immune-related SD (irSD), irPD, and immune-related Unevaluable (irUnevaluable) will be summarized.

### 7.5.6 Immune-related Progression-free Survival

Immune-related PFS (irPFS) is defined as the time from the start of treatment to the time of first documented progression per irRC, as determined by the Investigator or death due to any cause.

For the analysis of irPFS, the Kaplan-Meier method as defined in [Section 7.5.3](#) will be performed, and the same censoring rules as described in [Section 7.5.3](#) will be applied.

## 7.6 Safety Analysis

All safety analyses will be performed using the appropriate data for all patients in the SS unless otherwise stated.

### 7.6.1 Extent of Study Drug Exposure

Duration of exposure is defined as follows and will be summarized with descriptive statistics (n, mean, median, minimum, maximum).

ARRY-382:

**Duration of exposure** (days) = date of last (non-zero) dose of ARRY-382 – date of first dose of ARRY-382 + 1

Pembrolizumab:

**Duration of exposure** (weeks) = (date of last (non-zero) dose of pembrolizumab - date of first dose of pembrolizumab + 21)/7

Cumulative dose is defined as:

ARRY-382:

- **Planned cumulative dose** (mg) = sum of all protocol specified doses across each planned day of dosing
- **Actual cumulative dose** (mg) = sum of all actual doses taken during the dosing period

Pembrolizumab:

- **Planned cumulative dose** (mg/kg) = sum of all protocol specified doses across the dosing period
- **Actual cumulative dose** (mg/kg) = sum of all actual doses taken during the dosing period

The dose of pembrolizumab taken at each visit is calculated as total (planned and actual) dose administered (mg) at each visit / weight (kg) at that visit.

For patients who did not take any drug the actual cumulative dose is by definition equal to zero.

Dose intensity and relative dose intensity are defined as follows:

ARRY-382:

- **Planned dose intensity** (mg/day) = planned cumulative dose (mg) / [duration of exposure (days)]
- **Actual dose intensity** (mg/day) = actual cumulative dose (mg) / [duration of exposure (days)]
- **Relative dose intensity** = 100\*[actual dose intensity (mg/day) / planned dose intensity (mg/day)]

Pembrolizumab:

- **Planned dose intensity** (mg/kg/cycle) = planned cumulative dose (mg/kg) / [duration of exposure (weeks)/3]
- **Actual dose intensity** (mg/kg/cycle) = actual cumulative dose (mg/kg) / [duration of exposure (weeks)/3]
- **Relative dose intensity** = 100\*[actual dose intensity (mg/kg/cycle) / planned dose intensity (mg/kg/cycle)]

A summary of exposure, including duration, cumulative dose, actual dose intensity, and relative dose intensity (including categories <50%, 50%-<75%, 75%-<90%, 90%-<110%, and ≥110%, if applicable), will be presented for each study drug. Duration of exposure, cumulative dose, actual dose intensity, and relative dose intensity will also be listed for each patient.

### 7.6.1.1 Dose Modifications

#### **Dose reduction:**

Dose reductions are permitted for ARRY-382. A dose reduction is defined as a decrease in dose from the protocol planned dose and a decrease from the previous non-zero dose, even if this decrease has been directly preceded by an interruption.

If a patient's dose decreases from a higher than protocol planned dose to the planned dose, this is not counted as a reduction; however, if the dose is reduced directly from a higher than planned dose to a lower than protocol planned dose or the planned dose on a less frequent regimen, this is counted as a reduction.

If the dose on the first dosing record is lower than protocol planned dose this is also counted as a reduction.

Dose reduction will be summarized based on the dose modification data collected on the eCRF page.

### **Dose interruption:**

A dose interruption will be indicated in the eCRF by a dosing record with a total daily dose of 0 mg for one or more days.

Dose interruption will be summarized based on the dose modification data collected on the eCRF page. However, in order not to over count interruptions, dosing records with 0 mg entered as last dosing record will not be counted as interruptions. Those represent the reason for permanent discontinuation and will therefore be presented in the reason for treatment discontinuation analysis.

Frequency counts and percentages of patients who have dose reductions or any study drug interruptions, and the corresponding reasons, will be provided. The number of dose interruptions per patient, and the duration of dose interruptions (days) will also be summarized for each study drug.

### **7.6.2 Concomitant Medications**

Concomitant medications are defined as any medications (excluding study drug and prior anticancer treatments) and significant non-drug therapies (including physical therapy, herbal/natural medications and blood transfusions) administered in the study and recorded in the Prior and Concomitant Medications eCRF.

Concomitant medications will be coded using the latest version of the WHO Drug Reference Listing dictionary available at the time of reporting and will be summarized by ATC (level 2) and PT (level 4). These summaries will include:

1. medications starting on or after the start of study treatment but no later than 30 days after last dose of study treatment, and
2. medications starting prior to the start of study treatment and continuing after the start of study treatment.

All concomitant medications will be listed.

Incomplete dates will be handled as described in [Section 7.1.9.1](#).

### 7.6.3 Subsequent Anticancer Therapies

Subsequent anticancer therapies include anticancer systemic therapy, anticancer radiation or anticancer surgery.

Subsequent anticancer systemic therapy will be summarized by ATC class (level 2) and PT.

Subsequent anticancer systemic therapy, radiotherapy, and surgery will be listed.

Incomplete dates will be handled as described in [Section 7.1.9.6](#).

### 7.6.4 Adverse Events

AEs and serious adverse events (SAEs) will be coded by PT and SOC using the latest available MedDRA version.

The severity of an AE will be assessed by the investigator using the NCI CTCAE, Version 4.03. For patients with more than 1 AE within a SOC or PT, only the highest grade will be included in by-severity summaries.

The investigator will also assess whether the AE is suspected to be related to study drug (i.e., a treatment-related AE). For patients with more than 1 AE within a SOC or PT, the highest level of relationship (related is higher than not related) will be included in the by-relationship summaries.

For summaries by SOC and PT, each patient will be counted at most once per SOC and at most once per PT. For summaries by PT, each patient will be counted at most once per PT.

Treatment-emergent AEs (TEAEs) will be defined as:

- Any new event that starts after administration of study drug and  $\leq 30$  days after treatment discontinuation.
- Any event that was ongoing when treatment with study drug started and the severity/grade after treatment was higher than the Baseline value (fluctuations below the Baseline severity/grade are not considered as treatment emergent).
- Any new event that starts  $> 30$  days after treatment discontinuation and is assessed by the Investigator as related to study treatment.

Every effort should be made to obtain start dates for adverse events (AEs). If an AE is missing the start date, and the timing of the start date relative to treatment start is not known, it should be considered as treatment emergent for reporting and analysis purposes.

Unless otherwise stated, only TEAEs will be presented in summary tables. However, all AEs will be presented in listings.

Overall summary of safety table will include numbers and percentages of the following:

- Patients who died on study or within 30 days of last treatment
- Patients with at least 1 TEAE regardless of causality
- Patients with at least 1 treatment related TEAE
- Patients with treatment related TEAEs by worst severity
- Patients with at least 1 treatment-emergent SAE (TESAE)
- Patients with at least 1 treatment-related TESAE
- Patients who discontinued study drug due to a TEAE regardless of causality
- Patients who discontinued study drug due to a treatment-related TEAE
- Patients with a dose reduction due to a TEAE
- Patients with a dose interruption due to a TEAE

All TEAE summaries will be displayed (frequency counts and percentages) alphabetically by system organ class (SOC) and preferred term (PT) by descending frequency within SOC, if not otherwise noted. Individual summary tables showing the incidence of patients with the following subsets of TEAEs will be generated:

- TEAEs, regardless of causality, by SOC, PT and maximum severity
- TEAEs, regardless of causality, by SOC and PT
- TEAEs, regardless of causality, by PT
- Treatment-related TEAEs with suspected relationship to ARRY-382 by SOC, PT and maximum severity
- Treatment-related TEAEs with suspected relationship to pembrolizumab by SOC, PT and maximum severity
- Treatment-related TEAEs with suspected relationship to ARRY-382 by PT
- Treatment-related TEAEs with suspected relationship to pembrolizumab by PT
- TESAEs, regardless of causality, by SOC, PT and maximum severity
- TESAEs, regardless of causality, by SOC and PT
- TESAEs, regardless of causality, by PT
- TESAEs with suspected relationship to ARRY-382 by SOC, PT and maximum severity
- TESAEs with suspected relationship to pembrolizumab by SOC, PT and maximum severity

- TEAEs, regardless of causality, that led to discontinuation of study drug, by SOC and PT
- Treatment-related TEAEs with suspected relationship to ARRY-382 leading to study drug discontinuation by SOC and PT
- Treatment-related TEAEs with suspected relationship to pembrolizumab leading to study drug discontinuation by SOC and PT
- TEAEs that led to dose reduction in ARRY-382 by SOC and PT
- TEAEs that led to dose interruption /delay of ARRY-382 by SOC and PT
- TEAEs that led to dose interruption /delay of pembrolizumab by SOC and PT
- Non-serious TEAEs, regardless of causality, by SOC and PT
- TEAEs that resulted in death on study or within 30 days of last study treatment by SOC and PT

Separate listings for AEs, serious AEs (SAEs), AEs requiring dose interruption, AEs leading to any study drug discontinuation, and death recorded during the study will be provided.

All AEs and their attributes will be presented in data listings sorted by patient identifier, AE and date of onset of the AE.

### 7.6.5 Clinical Laboratory Evaluations

Required hematology, coagulation, clinical chemistry, thyroid panel and urinalysis tests are described in Table 9 of the protocol. Hematology, clinical chemistry, coagulation, thyroid panel and urinalysis test results will be presented using the International System of Units (SI units) and, where appropriate, will be graded using NCI CTCAE, Version 4.03.

For laboratory data, baseline is the last available assessment performed prior to the treatment start date/time. If more than one value is available, priority is given to the central assessment versus the local assessment. If more than one central sample is available, priority is given to the assessment marked as *Unscheduled* or *Repeat* assessment. Patients who start treatment and discontinue from the study on the same day may have 2 different sets of data collected on study day 1, one being reported to the cycle 1 day 1 visit, the other reported to the EOT visit. Data reported at the EOT visit are not eligible for baseline selection.

The following laboratory parameters will be summarized by CTCAE grade:

- Hematology:  
Hemoglobin (anemia/hemoglobin increased), Platelets (platelet count decreased), WBC (white blood cell decreased/increased), Neutrophils (neutrophil count decreased), Lymphocytes (lymphocyte count increased/decreased).
- Chemistry:

Albumin (hypoalbuminemia), Alkaline phosphatase (ALP) (alkaline phosphatase increased), Alanine aminotransferase (ALT) (ALT increased), Aspartate aminotransferase (AST) (AST increased), Total bilirubin (TBL) (blood bilirubin increased), Creatinine (creatinine increased), Corrected calcium (hypocalcemia/ hypercalcemia), Creatine Kinase (CPK increased), Glucose (hypoglycemia/hyperglycemia), Amylase (serum amylase increased), Lipase (lipase increased), Phosphate (hypophosphatemia), Magnesium (hypomagnesemia/hypermagnesemia), Potassium (hypokalemia/hyperkalemia), Sodium (hyponatremia/hypermnatremia).

- Coagulation: INR (INR increased), PTT or aPTT (Activated partial thromboplastin, time prolonged)

The following rules will be used for grading elevated glucose:

- If a glucose value falls within normal ranges it should be graded as zero, irrespective of fasting status.
- If fasting status is unknown and the result falls within the ranges for hyperglycemia grades 1 or 2, grade should be set to missing.
- If fasting status is known and fasting did not occur, and the result falls within the ranges for hyperglycemia grades 1 or 2, grade should be set to 0.

The following laboratory parameters will be summarized by normal range:

- Hematology:  
Hematocrit, RBC, Monocytes (absolute), Eosinophils (absolute), Basophils (absolute).
- Chemistry:  
Bicarbonate (CO2), BUN or urea, Chloride, Glucose (non-fasting), LDH, Total protein, Direct bilirubin.
- Urinalysis:  
Specific gravity, Glucose, Ketones, Blood, Nitrite, Leukocytes.
- Thyroid panel:  
Thyroid-Stimulating Hormone (TSH)  
Triiodothyronine (T3), free  
Thyroxine (T4), free

The Corrected Calcium will be derived from Calcium and Albumin results as per the following formula:

$$\text{Corrected calcium (mmol/L)} = [4 * \text{calcium (mmol/L)} - 0.8 * (0.1 * \text{albumin (g/L)} - 4)] / 4$$

The normal range of the Calcium will be used as normal range for Corrected Calcium.

The following summaries will be produced for the hematology, coagulation, clinical chemistry, thyroid panel and urinalysis laboratory data (by laboratory parameter):

- Shift tables using CTCAE grades to compare baseline to the worst post-baseline value for laboratory parameters with CTCAE grades. For the laboratory parameters like blood glucose where patients can be graded for decreased or increased values, the worst post-baseline CTCAE grade will be presented for decrease and increase separately (e.g. hyperglycemia and hypoglycemia). In the description of worst grade increase, a decrease of a grade  $\geq 1$  will be described as grade 0. The reciprocal will be applied for grade decrease categorization.
- Shift tables using low, normal, high (as well as low and high combined) classifications to compare baseline to the worst post-baseline value for laboratory parameters where CTCAE grades are not defined.
- The following listings will be produced for the laboratory data for all laboratory parameters where CTCAE grades are defined:
  - Listing of all laboratory data with values flagged to show the corresponding CTCAE grades and the classifications relative to the laboratory reference ranges.
  - Listing of patients with laboratory abnormalities of CTCAE grade 3 or 4.

Serology test results will be summarized.

All lab test results will be presented in listings sorted by patient identifier, lab test, and date/time of collection. Values outside laboratory normal ranges will be flagged where appropriate.

### **Hepatic Toxicity**

Hepatic toxicity will be assessed based on the following Liver Function Tests (LFTs): ALT, AST, ALP, and TBL.

LFTs will be summarized as follows:

- Frequency counts and percentages of patients having a newly occurring value in the categories in [Table 3](#) will be provided.

In addition, a listing of all LFTs values for patients having a newly occurring value in the categories presented in [Table 3](#) will be provided.

**Table 3: Hepatic Toxicity Criteria**

Parameter	Criterion
ALT	>3xULN; >5xULN; >8xULN;>10xULN;>20 ULN
AST	>3xULN; >5xULN; >8xULN>10xULN;>20 ULN
AT (ALT or AST)	>3xULN; >5xULN; >8xULN>10xULN;>20 ULN
TBL	>1.5xULN, >2xULN
ALP	>2xULN, >3xULN
AT & TBL	AT >3xULN & TBL >2xULN; AT >5xULN & TBL >2xULN; AT >10xULN & TBL >2xULN
ALP & TBL	ALP >3xULN & TBL >2xULN
AT & TBL & ALP	AT >3xULN & TBL >2xULN & ALP <2xULN

### 7.6.6 Pregnancy Tests

Results of all pregnancy tests will be presented in a data listing.

### 7.6.7 Vital Signs and Body Measurements

The following criteria define clinically notable vital sign abnormalities:

#### Clinically notable elevated values

- Systolic Blood Pressure (BP):  $\geq 160$  mmHg and an increase  $\geq 20$  mmHg from baseline
- Diastolic BP:  $\geq 100$  mmHg and an increase  $\geq 15$  mmHg from baseline
- Heart rate (collected as pulse rate in the vital signs eCRF):  $\geq 120$  bpm with increase from baseline of  $\geq 15$  bpm
- Weight: increase from baseline of  $\geq 10\%$
- Body temperature [C]:  $\geq 37.5$  C

#### Clinically notable low values

- Systolic BP:  $\leq 90$  mmHg with decrease from baseline of  $\geq 20$  mmHg
- Diastolic BP:  $\leq 50$  mmHg with decrease from baseline of  $\geq 15$  mmHg
- Heart rate (collected as pulse rate in the vital signs eCRF):  $\leq 50$  bpm with decrease from baseline of  $\geq 15$  bpm
- Weight:  $\geq 20\%$  decrease from baseline
- Body temperature [C]:  $\leq 36$  C

Number and percentage of patients with at least one post-baseline vital sign abnormality will be summarized.

Descriptive statistics will be tabulated for baseline and change from baseline to worst post-baseline value (both directions) for each vital sign parameter.

Patients with clinically notable vital sign abnormalities will be listed. All vital sign assessments will be listed by patient and vital sign parameter. Clinically notable values will also be flagged in this listing.

### 7.6.8 ECG

Potential effects of treatment with study drug on ECG parameters will be assessed by ECG interval analysis of heart rate, pulse rate, QRS, QT, and QT interval corrected for heart rate (QTc). Triplicate measurements will be obtained at each assessment according to the schedule of assessments in the protocol. Results from triplicate readings will be averaged.

The average of the machine-read triplicate ECG measurements collected closest to but prior to the first dose of study drug will serve as each patient's Baseline-QTc value for all post-dose comparisons. The QTcF data collected on the eCRF page will be used in the summary.

Data from ECGs will be listed, notable values will be flagged, and any other information collected will be listed as appropriate. The following summaries will be provided for each applicable ECG parameter:

- Frequency counts and percentages of patients having notable ECG values according to [Table 4](#).
- For each QT interval (QT, QTcF), shift tables based on notable QT interval categories ( $\leq 450$ ,  $>450 - \leq 480$ ,  $>480 - \leq 500$ ,  $>500$  ms) at baseline to the worst post-baseline value observed.

**Table 4: Criteria for Notable ECG Criteria**

Parameter	Criterion
QT, QTcF	increase from baseline $> 30$ ms
	increase from baseline $> 60$ ms
	new $> 450$ ms
	new $> 480$ ms
	new $> 500$ ms
Heart rate	Increase from baseline $> 25\%$ to a value $> 100$ bpm
	Decrease from baseline $> 25\%$ and to a value $< 50$ bpm

### **7.6.9 Physical Examinations**

Physical examination dates will be presented in a data listing. Any abnormal findings were to have been reported as AEs and will be reported in the appropriate AE listings and summary tables.

### **7.6.10 Eastern Cooperative Oncology Group Performance Status Performance Status**

Eastern Cooperative Oncology Group (ECOG) performance status is used to assess the physical health of patients, and ranges from 0 (most active) to 5 (dead). Frequency counts and percentages of patients in each score category will be provided by assessment visit.

In addition, the ECOG shift from baseline to highest score during the post-baseline period will be summarized.

ECOG performance status at each time point will be listed.

### **7.6.11 Clinically Significant Procedures**

All clinically significant procedures related to cancer while on study (from first dose through end of study) will be listed.

### **7.6.12 Transfusion**

Data on transfusions of blood products received while on study will be listed.

## **7.7 Pharmacokinetic Analysis**

The Pharmacokinetic Analysis Set will be used for all PK analysis, listings and figures. C1D1 is defined as single dose (i.e., first dose), and C2D1 is defined as steady state.

### **7.7.1 Plasma Concentrations of ARRY-382 and its three metabolites (AR00469099, AR00469100 and AR00470870)**

Plasma concentrations of ARRY-382 and its three metabolites (AR00469099, AR00469100 and AR00470870) will be collected and then determined using a validated bioanalytical method at the time points as specified in protocol. All plasma concentration values for each patient in the PK set will be included in the bioanalytical plasma concentration listings. Individual concentration records will be flagged for the affected visit if any of the following occur:

- a. Patient had vomiting within 4 hours following study drug administration on the day of series PK sampling.

- b. Plasma levels were not considered to be at steady-state (i.e. dosing was not performed for at least 4 consecutive days prior to C2D1).
- c. Subject received a higher or lower dose compared to planned treatment.
- d. PK sampling time was outside the allowed window or the elapsed time was not calculable.

The plasma concentrations of ARRY-382 and its three metabolites (AR00469099, AR00469100 and AR00470870) will be summarized by phases, dose levels and cohorts for all nominal time points, including predose (trough) concentrations for C1D15, C3D1, C4D1, C5D1 and C6D1, using the following descriptive statistics: n (number of patients with non-missing values), m (number of non-zero concentrations), arithmetic mean, standard deviation, coefficient of variation (CV), geometric mean, geometric standard deviation, geometric CV, minimum, median and maximum. An individual concentration-time data point be excluded from the calculation of summary statistics if any of the above flags [a-d] apply. For each time point, statistical values will only be calculated if at least two-thirds of the individual concentration data measured are above the limit of quantitation. BLQs will be set to zero for the calculation of arithmetic mean, SD, CV, minimum, median and maximum. For the calculation of geometric means and geometric CVs, BLQ concentrations will be replaced by  $\frac{1}{2}$  LLOQ. When greater than one-third of data points are BLQ, the means, standard deviations and CVs will be reported as not calculated (NC). When all data points are BLQ, the mean will be reported as BLQ and standard deviations and CVs will be reported as NC. If there are less than 3 values for calculation of standard deviation or CV, the value will be reported as NC.

The geometric mean with standard deviation plasma concentration-versus-time profiles will be presented graphically for each analyte using both linear and semi-logarithmic scales on C1D1 and C2D1 for Phase 1b/Part A and Phase 2. Geometric mean plasma concentrations will only be plotted for a specific time point if at least two-thirds of the concentrations are above the limit of quantitation and the actual time of sample collection was within the protocol-specified time window. Individual plasma concentration-time profiles will also be presented graphically using linear and semi-logarithmic scales by study day. For ease of presentation, nominal time will be used to present results in summary and actual time for individual figures.

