- r. Predose PK blood samples must be collected within 120 minutes prior to administration of ARRY-382. Postdose PK samples will be collected at 1hr (± 5 min), 2hr (± 10 min), 4hr (± 20 min), and 8hr (± 30 min) after administration of ARRY-382 on Cycle 1 Day 1 and Cycle 2 Day 1. Postdose PK samples should not be collected if ARRY-382 is on hold.
- s. Trough PK blood samples will be collected predose (i.e., within 120 minutes before administration of ARRY-382) on Cycle 1 Day 15 and Day 1 of Cycles 3 through 6. If ARRY-382 is being held, the trough PK blood sample should still be collected.
- t. Patients are to be contacted via telephone or electronic means for survival status and any subsequent anticancer therapies for 1 year after the date of the last patient's first visit.
- u. Pembrolizumab should be administered Q3W according to instructions in [Section 6.2.2](#).

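### The PK steady-state flag tests dosing only before C2D1, so troughs taken just after a hold can enter the C1D15 and C3D1–C6D1 summaries, and possibly AUCtau,ss

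*SAP*

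**What the plan says.** SAP 7.7 sets the reference days: "C1D1 is defined as single dose (i.e., first dose), and C2D1 is defined as steady state". SAP 7.7.1 then lists four flags and scopes them by visit: "Individual concentration records will be flagged for the affected visit if any of the following occur". Flag a concerns vomiting on a serial-sampling day. Flag b is the steady-state test: "Plasma levels were not considered to be at steady-state (i.e. dosing was not performed for at least 4 consecutive days prior to C2D1". Flag c reads "Subject received a higher or lower dose compared to planned treatment". Flag d concerns a sampling time outside its window or an elapsed time that cannot be calculated.

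The same section summarizes concentrations at all nominal times, "including predose (trough) concentrations for C1D15, C3D1, C4D1, C5D1 and C6D1". An individual value is "excluded from the calculation of summary statistics if any of the above flags [a-d] apply". For PK parameters, SAP 7.7.2 excludes on flags a to c only.

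Protocol Tables 10 and 11, footnote s, schedule the troughs "on Cycle 1 Day 15 and Day 1 of Cycles 3 through 6" and add: "If ARRY-382 is being held, the trough PK blood sample should still be collected". Protocol Table 8 (Section 6.3.2) provides, for certain Grade 2 events, that ARRY-382 is withheld and then restarted at the original dose.

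SAP Table 5 uses the C1D15 predose concentration as the concentration at the end of the dosing interval when AUCtau,ss is calculated, on the assumption that steady state has been reached.

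**The concern.** The only steady-state test is tied to one visit, and the troughs are summarized at five others. The protocol expects holds, and expects some patients to return at the same dose. A predose sample drawn at or soon after that return reflects the hold, not steady-state exposure on the assigned dose. If it is averaged with on-drug troughs, the visit summary understates exposure.

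The C1D15 sample matters most because it is used twice: in the trough table and as an input to AUCtau,ss. A patient held before C1D15 but dosed without a break in the days before C2D1 passes flag b, yet may contribute a washed-out end-of-interval value. AUC over the dosing interval and the metabolite-to-parent ratio are both named among the secondary PK endpoints (SAP 4.2).

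**Working it through.** The plan gives no figure to reproduce. The check has two parts: which flags catch which patient, and how low the missed values would be.

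**1. Flags against cases (visits C1D15 and C3D1–C6D1)**

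| Case | a | b | c | d |
|---|---|---|---|---|
| Still on hold on the visit day | no | no (names C2D1) | arguable: 0 mg is below plan | arguable: no dose follows, so the 120-minute predose window cannot be met |
| Restarted at a reduced dose before the sample | no | no | yes | no |
| Restarted at the planned dose on the visit day | no | no | not clearly: the dose given that day is as planned | no: the sample lies within 120 minutes before a dose and the elapsed time is calculable |
| Restarted at the planned dose 1–2 days earlier | no | no | not clearly | no |

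The last two rows are the gap. The PK set (SAP 5.5) does not close it: its exclusion works at patient level, and a hold directed by the protocol is not a deviation.

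**2. Size of a missed value**

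Inputs: median terminal half-life 18 h (C1D1) and 19 h (C1D15) from Study 101 (Protocol 2.2.2.2), midpoint 18.5 h; once-daily dosing. Assumption: mono-exponential decline. The fraction remaining per 24 h is q = 2^(−24/18.5) = 0.407.

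- Restart on the visit day after m held doses, trough relative to steady state = q^m. For m = 2: 0.407² = 0.17. For m = 3: 0.407³ = 0.067.
- Full washout, then m resumed doses = 1 − q^m. For m = 1: 0.59. For m = 2: 0.83.
- Over 18 to 19 h these become 0.16–0.17, 0.06–0.07, 0.60–0.58 and 0.84–0.83.
- Four resumed daily doses: 1 − 0.407⁴ = 0.97. The SAP's own 4-day window is therefore adequate at any trough visit.

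**3. Effect on a visit summary (illustration)**

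The documents do not give the number of patients on hold. Part A dose groups had 6 or 7 patients (Protocol 2.3.1). Suppose one of 6 has a trough at 0.067 of the others, which are all equal.

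- Arithmetic mean: (5 + 0.067)/6 = 0.84 of the on-drug value.
- Geometric mean: 0.067^(1/6) = 0.64.
- One of 23 (the planned prOVCA size): (22 + 0.067)/23 = 0.96 and 0.067^(1/23) = 0.89.

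The rule that two-thirds of values must be quantifiable would not stop this, since 5 of 6 or 22 of 23 still qualify even if the odd value is below the limit.

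**4. Effect on AUCtau,ss (illustration)**

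Serial samples stop at 8 h, so the 8–24 h segment rests on the C1D15 value. By the log-down rule its area is (C8 − C24) × 16 / ln(C8/C24). With C24/C8 = 2^(−16/18.5) = 0.549 the area is 0.451 × 16/0.600 = 12.0 × C8. If C24 is only 0.067 of its proper value, C24/C8 = 0.037 and the area is 0.963 × 16/3.30 = 4.7 × C8, about 39% of the proper segment. The 0–8 h part is unaffected, so the loss in the whole AUCtau,ss is smaller and cannot be sized without the concentration profile.

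**The case against.** The strongest reply is that flags c and d already do most of this work. Protocol 7.4 allows a trough only within 120 minutes before ARRY-382 is given. During a hold nothing is given, so flag d can be read to exclude the sample. Flag c names no visit, and the SAP treats 0 mg as a recorded dose (SAP 7.1.4 and 7.6.1.1), which is below plan. A reader might infer from footnote s that every sample drawn during a hold goes into the summaries. The documents do not support that, because a reasonable programmer could exclude those samples under either flag. The text does not say so, however, and SAP 7.6.1.1 treats interruption separately from reduction. Flag d is also not among the exclusions for PK parameters.

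Two other strong readings fail. One is that the distortion would be greatest at later cycles and look like falling exposure: the documents give no hold frequency by cycle. The other is that the Ctrough,ss parameter itself is compromised: Table 5 lists it under C2D1, the visit that flag b covers.

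It can also be said that the steady-state assumption in Table 5 is itself a condition on using the C1D15 value. That is possible, but no test of it is given for that visit, so the effect on AUCtau,ss is only possible.

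Finally, the residual case is narrow, the half-life is a parent-drug median from the monotherapy study, and no metabolite half-life is given although four analytes are summarized. The SAP cites protocol Version 5, while the protocol at hand is Version 4. These points limit the size of the problem but do not remove it.

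**Conclusion.** The gap is real but narrow. As written, flags a to d do not clearly catch a patient who returns to the planned dose on the visit day, or one or two days before, at C1D15 or C3D1–C6D1. Such values would sit at roughly 7% to 83% of steady state, depending on the length of the hold and the time since restart. One of them among six patients could take the geometric mean trough to about 0.64 of its on-drug value. AUCtau,ss and its metabolite ratio may be affected through the C1D15 value.

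For samples drawn during a continuing hold the problem is unclear wording, not a demonstrated error. The sizes assume mono-exponential decline at 18 to 19 h and an illustrative number of affected patients. No primary endpoint, decision rule, sample size or error rate depends on this. It is a minor clarification to descriptive secondary PK.

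**What to change.** In SAP 7.7.1, reword flag b so that it applies at every predose visit (C1D15 and C2D1 to C6D1), using the existing 4-consecutive-day window counted back from that sample. State three things with it:

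- A held (0 mg) day within the window triggers the flag. This also settles whether the present wording means four days of uninterrupted dosing or a gap of four days.
- The flag applies to the C1D15 value before it is used for AUCtau,ss in Table 5, and therefore to the metabolite ratio built on it.
- All flagged values stay in the listings.

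The wording should also say how a patient on a reduced dose is handled, so that flags b and c agree.

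The change is a sentence or two in the SAP and uses dosing records already collected. The price is some loss of usable data. A patient who missed only the dose four days before the sample would be excluded with a trough of 1 − 0.593 × 0.407³ = 0.96 of steady state. In groups of 6 or 7 a few such exclusions matter, because SD and CV are not reported below three values. No study procedure changes.
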